- 1. **High resistance IMT.** Participants will be given a device and taught to do the IMT using the hand held device and instructed to train twice per day (30 breaths each time) for a minimum of two weeks. Participants will be taught to increase the load resistance on their device based on their breathing effort which they will self-assess using a scale. If they have a longer wait, they can continue doing the exercises until the operation.
- 2. **Low resistance IMT.** Participants will do the same as for the high intensity group, but the device will be set to a training load that will not change the strength or endurance of the inspiratory muscles. It is important that participants in this group believe that they are actually training, as the aim of this group is to account for any "placebo" effect, thereby ensuring that any reduction in lung complications in the high intensity group is "real".
- 3. **Usual care.** Participants will be given advice about the importance of deep breathing exercises and a leaflet instructing them how to do these exercises, but will otherwise have no additional breathing training before surgery.

The clinical team looking after patients at the time of surgery will not know to which group a patient has been allocated. We will measure the strength of the inspiratory breath when a

patient agrees to take part and immediately before the operation in all three groups, so that we can determine which type of breathing exercises work. In the high and low resistance IMT groups, we will monitor how much training patients were able to complete in the two weeks prior to surgery by asking them to complete a diary of their training (the number of training sessions and duration of each session is recorded automatically on the device).

The main aim of the study is to compare the number of lung complications between the three groups in the first 30 days after surgery. We will record whether a lung complication develops in hospital whilst patients are recovering from surgery or causes hospital admissions after patients are discharged from hospital following their operation. We will also compare the time patients spend in hospital, their quality of life after their operation and survival.

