#### 5.6.3.2 High resistance IMT training protocol

The mode of delivery of the high resistance IMT intervention in the main study will be contingent on the results of the SWAT with regards to the need for an additional face-to-face visit and manual vs. automatic load adjustment on the IMT device (section 5.2).

We will use a modified version of the IMT intervention protocol used in the recent study by Valkenet et al [23] (based on the protocol of Bailey et al [32]). Participants will undertake a maximum of 30 breaths (or as many breaths as can be tolerated), twice daily, 7 days per week, using the POWERbreathe® KHP2 at home. The initial training load for participants in the high intensity IMT arm will be set by the research nurse or physiotherapist at the first face-to-face meeting (section 5.6.3.1).

Training intensity will commence at 50% of MIP. If the patient cannot tolerate this, the load will be titrated to the maximum level that the patient can tolerate for at least 20 breaths (30 breaths is the maximum tolerable load) aiming for a starting workload of at least 40% of MIP. During the subsequent training intervention the load will be increased in accordance with tolerability quantified using rate of perceived exertion scale (a modified Borg exertion scale) which quantifies the perceived exertion of breathing from 0 to 10 ("How intense was the training session?") [30, 31]. Participants will refer to the RPE rating scale and rate their perceived exertion in their paper training diary after each training session.

Participants in Phase 1 who are randomised to the 'manual load adjustment' group will be given a table of pre-calculated training loads (Figure 3) to allow them to increase the load on their device by 5% if their perceived exertion at the end of a training session is 5 or less (using the RPE rating scale as shown in Figure 2).

Participants in Phase 1 who are randomised to the 'automatic load adjustment' group will be taught how to perform the first 3 test breaths using the IMT device which will automatically estimate MIP and adjust to the correct load. Participants in the 'automatic load adjustment' group will also record their perceived exertion using the RPE rating scale.

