# 6.4 Duration of treatment period

The duration of the treatment commences when the participant receives face to face training on breathing exercise regimens in all three arms; high resistance IMT, low resistance IMT or usual care. The duration of the breathing exercises will be for a minimum of two weeks before the day of surgery. In some instances the surgery date may be cancelled or postponed; in such instances, the duration of treatment will be extended further until an alternative surgery date is confirmed. For non-cancer surgery (e.g. elective heart surgery), the waiting time between referral for surgery and surgery may be longer than 2 weeks; therefore, participants will be recruited as soon as feasible and may be required to perform the intervention for up to 8 weeks before the day of surgery.

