#### SWAT primary outcome

The primary outcome of the SWAT will be the progression in training load from baseline. The secondary outcomes will be:

- Change in work (recorded on the IMT device) from baseline;
- · Change in MIP from baseline;
- Change in spirometry markers (FEV1 and FVC) from baseline;

- Proportion of participants following at least 80% of the planned training sessions;
- Proportion of participants training at the prescribed intensity score of (RPE rating ) ≥5.

We will consider removing the additional 'virtual' follow up meeting in Phase 2 if the increase in training load from baseline in the no additional 'virtual' follow up meeting group is similar to that in the additional 'virtual' follow up meeting group. We will consider automatic load adjustment in Phase 2 if the increase in training load from baseline in the automatic group is similar to that of the manual group. We will take into account any important interactions between the two interventions (loading method with or without an extra 'virtual' follow up meeting) when making the final decision regarding the delivery of the intervention in Phase 2.

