## **SWAT** secondary outcomes

- Change in work (recorded on the IMT device) from baseline;
- Change in MIP from baseline;
- Change in spirometry markers (FEV1 and FVC) from baseline;
- Proportion of participants following at least 80% of the planned training sessions;
- Proportion of participants training at the prescribed intensity score of (RPE rating) ≥5

New variable	Rules
Change in load	

load on last line of patients diary – load at initial training visit

Change in work	

work in joules on last line of patients diary – work in joules at initial training visit

Change in MIP	= MIP on day of surgery – MIP at baseline
Change in spirometry markers (FEV 1 and	= FEV 1 on day of surgery – FEV 1 at baseline
FVC) from baseline	= FVC on day of surgery – FVC at baseline
Proportion of participants following at least 80% of the planned training sessions – recorded on patient diary	YES: If more than 22 (80% of planned 28) energy measurements are recorded on the patient diary
	NO: If 22 or less (80% of planned 28) energy measurements are recorded on the patient diary
	MISSING: otherwise
Proportion of participants following at least 80% of the planned training sessions – recorded on KHP2 device	YES: If more than 22 (80% of planned 28) energy measurements are recorded on the KHP2 device
	NO: If 22 or less (80% of planned 28) energy measurements are recorded on the KHP2 device
	MISSING: otherwise
Proportion of participants training at the prescribed intensity score of RPE rating ≥5	YES: If participant reported an RPE of 5 and above on their first, second and last line of patients diary
	NO: If participant reported at least one RPE below 5 on their first, second or last line of patients diary
	MISSING: otherwise
Proportion of participants training at the prescribed intensity score of RPE rating ≥5 – additional visit measurements	YES: If participant reported all RPE values of and above during the most recent 10 training sessions at their additional visit

(participants randomised to additional visit only)

**NO:** If participant reported at least one RPE below 5 during the most recent 10 training sessions at their additional visit

MISSING: otherwise

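### The SWAT 80%-of-sessions outcome counts sessions over the whole wait for surgery against a fixed two-week plan of 28, so it overstates adherence for participants who wait longer than two weeks

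*SAP*

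**What the plan says.** SAP 2.1.2 lists as a SWAT secondary outcome the "Proportion of participants following at least 80% of the planned training sessions". The derivation table in SAP 4.3.2 gives two versions. The device version is YES "If more than 22 (80% of planned 28) energy measurements are recorded on the KHP2 device"; the diary version is YES "If more than 22 (80% of planned 28) energy measurements are recorded on the patient diary". Neither has a start date, an end date or an adjustment for time to surgery.

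Protocol 5.6.3.2 sets high resistance training at "twice daily, 7 days per week". On duration, Protocol 6.4 says: "The duration of the breathing exercises will be for a minimum of two weeks before the day of surgery". If surgery is cancelled or postponed, "the duration of treatment will be extended further until an alternative surgery date is confirmed". Participants awaiting non-cancer surgery "may be required to perform the intervention for up to 8 weeks before the day of surgery". SAP Table A8 lists training of under 2 weeks and of over 8 weeks as deviations, so anything between the two is within plan.

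The Protocol's Trial summary is softer: "If they have a longer wait, they can continue doing the exercises until the operation". It also describes monitoring the training completed over the last two weeks before the operation. The SAP rule does not use that window.

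**The concern.** The denominator covers 14 days, while the numerator can cover the whole wait. A participant who waits longer has more days in which to collect the same 23 sessions, so the pass mark falls as the wait grows. The result no longer matches its label.

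SAP 2.1.1 makes describing adherence a purpose of Phase 1, and this outcome is one of the ways in which the four SWAT cells are compared on it. At stake are the reported level of session adherence and, if waits are long, how clearly the cells can be told apart. Because the outcome is only tabulated, no model or sensitivity analysis would correct the figure later.

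**Working it through.** **The SAP's own figure.** Twice daily for 14 days gives 2 × 14 = 28 sessions. 0.80 × 28 = 22.4, so the smallest passing whole number is 23 (23/28 = 82.1%; 22/28 = 78.6%). More than 22 is therefore the correct cut-off for a 14-day plan.

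**Reading 1: training is planned up to surgery.** Scheduled sessions are 14 × weeks, and the share needed to pass is 23/(14 × weeks).

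| Wait (weeks) | Scheduled | 80% mark | 23 sessions as % of schedule |
|---|---|---|---|
| 2 | 28 | 23 | 82.1 |
| 3 | 42 | 34 | 54.8 |
| 4 | 56 | 45 | 41.1 |
| 6 | 84 | 68 | 27.4 |
| 8 | 112 | 90 | 20.5 |

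At two sessions a day the 23rd falls on day 12 (23/2 = 11.5). A participant could stop there and still score YES whatever the wait.

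**Reading 2: only the two-week minimum is planned.** Then 28 is the right denominator, but the count should stop after 14 days. Someone who waits 4 weeks and trains once a day does 14 sessions in any 14-day window (14/28 = 50%), yet has 28 recorded and scores YES.

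**Direction.** For waits of 14 days or more the error goes one way. Anyone who truly reaches 80% under either reading has at least 23 sessions and passes; the misclassified are all false passes.

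**Size.** The documents give neither the distribution of waits nor that of completion, so both are assumed. Each participant has a completion probability drawn from beta(2.6, 1.4), mean 2.6/4.0 = 65%. Sessions are binomial(2 × days, that probability), and waits are uniform over the range shown.

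| Waits (days) | Rule reports | Truly at least 80% of sessions to surgery |
|---|---|---|
| 14–21 | 53% | 31% |
| 14–28 | 65% | 31% |
| 14–56 | 84% | 30% |

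Counting only a 14-day window, the true share is about 30% in every row, so the overstatement is similar under Reading 2.

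**Difference between cells.** I repeated this for two groups with mean completion 55%, beta(2.2, 1.8), and 75%, beta(3.0, 1.0). The true gap, on sessions to surgery, is about 33 points throughout (roughly 17% against 50%). The rule shows 73% against 91%, a gap of 18 points, for waits of 14–56 days; 50% against 79%, a gap of 29, for 14–28 days; and 37% against 70%, a gap of 33, for 14–21 days. Compression therefore appears only as waits lengthen.

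**The case against.** The strongest defence is that the SAP states its plan openly as 28 sessions, which is the two-week minimum, and that the Trial summary treats later training as something participants can do rather than must do. On that reading the denominator is right. This much stands: a reader might infer that participants generally pass after a fifth of their sessions, and the documents do not support that. The 21% figure needs an 8-week wait with twice-daily sessions planned throughout, and the Protocol is mixed on whether they are. The defence does not supply the missing window, however, so the rule is still wrong under its own reading.

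A reader might also infer that the outcome mainly measures waiting time. That is not supported either. Even with waits of 14–56 days, the simulated pass rate rises from 0.43 to 0.87 as completion goes from 30% to 60%. With waits of 14–21 days, someone completing 40% passes with probability only about 0.01, against 0.65 for 14–56 days.

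The consequences are limited in four further ways, and all of these stand.
- SAP 4.4.3 tabulates SWAT secondary outcomes without modelling them. The SWAT primary outcome, load progression, does not use this rule.
- The progression criterion on adherence uses a separate per-week variable, IMT adherence, so the rule does not bear on it.
- SAP 1.1.2 records that the study closed at the end of Phase 1, so no Phase 2 delivery choice depends on the result.
- SWAT allocation is randomised within centre and specialty (Protocol 6.1), so waits should be roughly balanced across cells. The distortion is of level and sensitivity, and does not favour one delivery mode. Table A9 will also show days from randomisation to surgery.

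Finally, it is tempting to add that anyone operated on within 11 days cannot reach 23 sessions (2 × 11 = 22). Eligibility requires at least 14 days to planned surgery, and under two weeks of training is a listed deviation, so scoring NO is consistent with a plan of 28.

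**Conclusion.** The concern holds. The rule matches its label only for a 14-day training period. For longer waits it lowers the pass mark under one reading of the plan, and counts sessions from outside the planned period under the other. In both cases the reported proportion is too high.

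The overstatement is about 22 points for waits of 14–21 days (53 − 31), 34 for 14–28 days (65 − 31) and 54 for 14–56 days (84 − 30). These figures rest on the assumed beta distribution, uniform waits and a constant completion rate over time; only the share-of-schedule table is free of such assumptions. Differences between SWAT cells are compressed materially only if waits are long.

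The duration text used here is from Protocol version 2.0, whereas the SAP cites version 3.0. The 8-week limit in SAP Table A8 agrees with the text used. Severity is minor to moderate: a mislabelled, unmodelled SWAT secondary outcome.

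**What to change.** Make numerator and denominator cover the same period, in both the diary and the device versions. Either of two forms will do.

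1. Count only sessions inside one named 14-day window, against 28. State whether this is the first 14 days after the training visit or the last 14 before surgery, and reconcile the choice with the pre-operative two-week monitoring described in the Protocol's Trial summary.
2. Score YES when sessions done / (2 × days from training visit to surgery) is at least 0.80.

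Label the outcome and its row in Table A10 to match the form chosen. Report the other form beside it where the records allow: form 1 needs session dates, while form 2 needs only a total and two dates. The SAP should also say which sessions it treats as planned, since Protocol 6.4 and the Trial summary differ on whether training beyond two weeks is required or optional; those passages should be reconciled.

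The cost is SAP wording and code, with no new data collection if dates or totals are already held. The reported proportion will be less favourable. Form 1 alone says nothing about adherence outside its window, which is the reason to show both.

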#### ii) Manual load adjustment to increase training load

Participants will increase the training load manually based on their perceived exertion measured using the RPE rating scale. An RPE rating at the end of a training session of 5 or less will signify that the load should be increased by 5% (participants will be supplied with a table of precalculated training loads as shown in Figure 3). Participants will record training sessions and RPE ratings in the paper diary.

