#### 5.2.3 SWAT primary outcome

The primary outcome of the SWAT will be the progression in training load from baseline. The secondary outcomes will be:

- Change in work (recorded on the IMT device) from baseline;
- Change in MIP from baseline;
- Change in spirometry markers (FEV1 and FVC) from baseline;
- Proportion of participants following at least 80% of the planned training sessions;

• Proportion of participants training at the prescribed intensity score of (RPE rating ) ≥5.

We will consider removing the additional face-to-face visit in Phase 2 if the increase in training load from baseline in the no additional visit group is similar to that in the additional visit group. We will consider automatic load adjustment in Phase 2 if the increase training load from baseline in the automatic group is similar to that of the manual group. We will take into account any important interactions between the two interventions (loading method with or without an extra visit) when making the final decision regarding the delivery of the intervention in Phase 2.

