# Automatic load adjustment (using the automatic function on the IMT device to increase training load) vs. manual increase of training load

i) Automatic load adjusting function to increase training load

Participants will make use of the automatic load adjusting function on the IMT device to increase the training load in response to training adaptation, i.e. MIP is estimated at the beginning of each training session and the training load is adjusted automatically by the device, without the user having to increase the training load manually. Participants will record training sessions in the paper diary and rate the intensity of each training session using the RPE rating scale for ratings of perceived exertion (RPE rating scale from 0-10) which can be found in the appendix (Figure 2).

ii) Manual load adjustment to increase training load

Participants will increase the training load manually based on their perceived exertion measured using the RPE rating scale. An RPE rating at the end of a training session of 5 or less will signify that the load should be increased by 5% (participants will be supplied with a table of precalculated training loads as shown in Figure 3). Participants will record training sessions and RPE ratings in the paper diary.

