#### Additional 'virtual' follow up meeting vs no additional 'virtual' follow up meeting

i) One additional 'virtual' follow up meeting

Participants in the high resistance IMT group will receive an additional follow up meeting conducted via telephone or video call within one week of the initial IMT training session (ideally day 3 to 5). The research nurse or physiotherapist will assess adherence and progression of the training load and will provide further training or support where it is required (section 5.6.3). Participants will have been provided with and may have watched a step-by-step digital recording (video) on how to use the device at the initial IMT training session and will have also been provided with written information, a paper training diary for recording training sessions, and telephone support in the form of a helpline number that participants can call (if they have any queries or require assistance). Within the training diary they will be asked to rate their perceived exertion using the RPE rating scale after each training session.

ii) No additional 'virtual' follow up meeting

Participants will attend the initial IMT training session with a research nurse or physiotherapist but participants will not receive an additional virtual follow up meeting.

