**Table A8: Protocol deviations** 

	Cai	rdiac	Non-c	ardiac	Ove	erall
	n	%	n	%	n	%
Non-adherence to the intervention						
Intervention not delivered per protocol						
Less than 2 weeks IMT training						
More than 8 weeks IMT training						
Missed all training						
More training than recommended (>2x 15min sessions/d)						
Continue training after surgery						
Not training at the recommended intensity (high resistance IMT group only)						
Other monitoring of study intervention						
Undergone surgery prior to completing the intervention						
Surgery delayed because of intervention						
Other non-compliance						
Ineligible but randomised						
Did not receive allocated intervention (cross- over)						

Table to be repeated with participants grouped by randomised allocation

Table A9: Details on randomisation and intervention timings

	Car	diac	Non-c	ardiac	Overall		
	n	%	n	%	n	%	
Days between randomisation and surgery (Median, IQR)							

Table to be repeated with participants grouped by randomised allocation

Section 3: Primary and secondary outcomes

Table A10: SWAT primary and secondary outcomes

		Automatic load + Additional visit (n=XX)	Manual load + Additional visit (n=XX)	Automatic load + No additional visit (n=XX)	Manual load + No additional visit (n=XX)
PRIMARY OUTC	OME				
Training load	Baseline				
	Day of surgery*				
	Change from baseline				
SECONDARY OL	ITCOMES				
Work	Baseline				
	Day of surgery*				
	Change from baseline				
MIP	Baseline				
	Day of surgery				
	Change from baseline				
FEV 1	Baseline				
	Day of surgery				
	Change from baseline				
FVC	Baseline				
	Day of surgery				
	Change from baseline				

Inspire SAP, version v0.3 05/07/2024
In accordance with v3.0 of the study protocol

Proportion of participants following at least 80% of the planned training sessions

Recorded on patient diary

Recorded on KHP2 device

Proportion of participants training at the prescribed intensity score of (RPE rating )

First, second and last line of patients diary

Most recent 10 sessions at additional visit

(participants randomised to additional visit only)

Table A11: Primary and secondary outcomes

Outcome	Randomised to IMT (n=xx)	Randomised to Sham IMT/Usual care (n=xx)	Randomised to Sham IMT (n=xx)	Randomised to usual care (n=xx)	Effect (95% CI)*	p-value
Any PPC					RD/RR	
Respiratory infection					-	-
Respiratory failure					-	-
Pleural effusion					-	-
Atelectasis					-	-
Pneumothorax					-	-
Bronchospasm						

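### The SWAT prescribed-intensity row requires RPE 5 or more on the first, second and last diary lines together, so it cannot separate a low start from a low finish

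*SAP*

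**What the plan says.** Protocol 5.2.3 lists the outcome as "Proportion of participants training at the prescribed intensity score of (RPE rating ) ≥5". It names no sessions and no time point, and SAP 2.1.2 repeats it in the same general form.

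The derivation table in SAP 4.3.2 (SWAT secondary outcomes) supplies the rule. YES is given "If participant reported an RPE of 5 and above on their first, second and last line of patients diary". NO is given "If participant reported at least one RPE below 5 on their first, second or last line of patients diary". Table A10 carries this as a single row, "First, second and last line of patients diary", for the four SWAT groups.

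The ratings arise as follows:

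- **Starting load.** Protocol 5.6.3.2: "Training intensity will commence at 50% of MIP". It may be titrated down if not tolerated. No upward step at the start is described for a low rating.
- **Manual groups.** Protocol 5.2.2: "An RPE rating at the end of a training session of 5 or less will signify that the load should be increased by 5" per cent. SAP 2.1.2 has the same rule.
- **Automatic groups.** SAP 2.1.2: "MIP is estimated at the beginning of each training session and the training load is adjusted automatically by the device".
- **Diary.** SAP 2.1.2 asks participants to "rate their perceived exertion using the RPE rating scale after each training session". Protocol 5.6.3.2 sets two sessions a day.
- **Additional contact.** SAP 2.1.2 places it within a week of the initial session, ideally on day 3 to 5.

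Table A10 has one other RPE row. It covers only participants randomised to the additional contact, and it looks back over sessions before that contact. SAP 4.4.3 says that SWAT secondary outcomes are tabulated by the factorial groups and not modelled.

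**The concern.** The rule joins two different things in one all-or-nothing flag: how hard the starting load felt, and how hard training felt at the end. The first depends largely on a load set from MIP before any adjustment. The second is what load progression and the additional contact are meant to influence.

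In the manual groups a rating below 5 at the start is a foreseen event with a planned response. A participant who rates 4, raises the load as instructed and trains at 5 or more from then on has followed the protocol, yet the row records NO. In the automatic groups the device sets the load from estimated MIP, and the same scoring applies to anyone who finds the start easy.

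The composite is the only perceived-intensity result that covers all four SWAT groups. A reader of Table A10 cannot tell whether a NO reflects a low start or a low finish. Of the ratings used in the two RPE rows, only the last diary line normally comes after the additional contact, and neither row shows it alone.

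**Working it through.** The plan gives no figure for this outcome, so there is none to reproduce. The check applies the rule as written.

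**Step 1. The rule.** Let F, S and L be the RPE ratings on the first, second and last lines. The row scores YES if min(F, S, L) ≥ 5.

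| F, S, L | SAP row | Last line alone |
|---|---|---|
| 3, 4, 7 | NO | YES |
| 3, 3, 3 | NO | NO |
| 4, 5, 6 | NO | YES |
| 6, 6, 4 | NO | NO |
| 5, 5, 5 | YES | YES |

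The first two participants differ in the way the SWAT would want to see, and they score the same. If F or S is below 5, no value of L gives YES. The fourth participant started at target and finished below it, and is also NO.

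**Step 2. Timing.** At two sessions a day, lines 1 and 2 fall at about day 1 if each line is one session. The contact is ideally on day 3 to 5. L is then normally the only one of the three ratings that can respond to it.

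**Step 3. Bounds.** Let p1, p2 and pL be the proportions at RPE 5 or more on the three lines. Then

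max(0, p1 + p2 + pL − 2) ≤ row proportion ≤ min(p1, p2, pL).

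Take the planned 40 per cell (SAP 2.4.2) and an assumed pL of 0.90 (36 of 40):

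| Assumed p1 = p2 | Lower bound | Upper bound |
|---|---|---|
| 0.50 | max(0, −0.10) = 0, or 0 of 40 | 0.50, or 20 of 40 |
| 0.70 | 0.30, or 12 of 40 | 0.70, or 28 of 40 |
| 0.90 | 0.70, or 28 of 40 | 0.90, or 36 of 40 |

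The same last-line result fits very different row values. If nearly everyone starts at 5 or more, the row comes close to the last line and little is lost.

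**Step 4. A contact effect on the last line.** Let q be the share with both early lines at 5 or more. Randomisation makes q the same in expectation with and without the contact. Let dH be the contact's effect on the last-line proportion among those participants, and dL its effect among the rest. Then

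- last-line difference = q × dH + (1 − q) × dL
- row difference = q × dH.

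The row drops the second term. Suppose the last-line proportions are 60% and 80%, and early ratings are independent of the last, so that dH = dL = 20 points:

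| Assumed q | Row, without vs with contact | Row difference | Last-line difference |
|---|---|---|---|
| 0.3 | 18% vs 24% | 6 points | 20 points |
| 0.5 | 30% vs 40% | 10 points | 20 points |
| 0.9 | 54% vs 72% | 18 points | 20 points |

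Other assumptions give other answers. With dL = 0 nothing is lost, and with dH = 0 the row shows no difference. The documents give neither q nor the split between dH and dL, so these figures show the mechanism and are not estimates.

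**The case against.** The best defence is that the row was never meant to show change. Its name concerns the conduct of training. Where the SAP wants change it says so, with change in load (the SWAT primary outcome, and the only SWAT outcome modelled), work, MIP and spirometry. As the protocol fixes no sessions, being at intensity at every sampled point is a coherent strict reading. This stands as far as it goes: the rule does not contradict the protocol. But the SAP does not label the row in that way, and on that reading too a NO cannot be traced to the start or the finish.

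There are also limits on the evidence. The diary form is not in the documents, so taking lines 1 and 2 as the first two sessions is a natural inference and not a stated fact. The 50% starting load comes from protocol version 2.0, whereas the SAP says it follows version 3.0. The last line is a single session, and for someone who stops early it may fall well before surgery or even before the contact. Table A10's footnote already allows for last lines more than 7 days before surgery. These points argue for careful labels. They do not rescue the composite.

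A reader might infer more: that the row biases the comparison between SWAT groups, or that it would erase a real effect of the contact. The documents support neither. The same rule applies to all four groups, and Step 4 shows that the loss can range from none to complete depending on quantities that are not given.

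**Conclusion.** The point holds and is minor. What the rule does is certain from its text: anyone below RPE 5 on the first or second line is NO whatever follows, and a low start cannot be told from a low finish. That the hidden last line is normally the only rating after the contact rests on the diary having one line per session and on the contact taking place near its ideal time.

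The practical effect is unknown and may be small, because the documents contain no early RPE data. If the contact changes last-line RPE among participants who started low, the row leaves that part out, by an amount that cannot be estimated from the documents.

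It would be wrong to infer that a delivery decision is at risk. Recruitment ended with Phase 1 (SAP 1.1.2), the Phase 2 considerations in SAP 2.1.2 rest on training load, and this outcome is tabulated only.

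**What to change.** In SAP 4.3.2 and Table A10, show the proportion at RPE 5 or more separately for the first, second and last diary lines, by SWAT group. Use neutral labels: 'first session recorded', 'second session recorded' and 'last session recorded'. Avoid a label that implies a final achieved intensity, since the diary may stop early. Extend the existing last-line timing footnote, now attached to training load and work, to the last-session row. If the composite is wanted, keep it as a further row labelled 'RPE 5 or more at all three lines'.

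The cost is two more rows in Table A10, or three with the composite kept, and matching wording in 4.3.2. The current rule already needs all three ratings, so no new data are required. The SAP supplied is marked v0.3, and its section 7 provides for documenting changes with a justification. One limit remains: each row describes a single session and not the whole course of training.
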